## 1. Study Objectives

The primary objective of this study is to evaluate the efficacy of laser acupuncture in reducing uremic pruritus in patients undergoing hemodialysis.

Secondary objectives include assessment of symptom severity, quality of life, and treatment safety.

## 2. Study Design

This is a prospective, randomized, controlled clinical study. Eligible participants will be allocated to intervention or control groups according to the study protocol. The study duration and assessment schedule are predefined.

## 3. Participants

**Inclusion criteria** include adult patients undergoing maintenance hemodialysis with clinically significant uremic pruritus.

**Exclusion criteria** include severe comorbid conditions or contraindications to laser acupuncture.

## 4. Interventions

Participants in the intervention group will receive laser acupuncture at predefined acupoints according to a standardized protocol.

The control group will receive usual care or sham treatment as specified.

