## 5. Outcome Measures

The **primary outcome** is change in pruritus severity measured by validated scales.

**Secondary outcomes** include quality-of-life measures and adverse events.

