### 6.2 Primary Outcome Analysis

The primary outcome will be analyzed using appropriate statistical tests based on data distribution. Between-group comparisons will be performed to evaluate treatment effects.

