## **6.5 Significance Level and Statistical Software**

All statistical tests will be two-sided with a significance level of 0.05. Statistical analyses will be conducted using standard statistical software.

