# **7. Ethical Considerations**

The study will be conducted in accordance with ethical principles and has received approval from the appropriate institutional review board.

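### Does leaving the control as usual care or sham make the primary comparison uninterpretable?

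*Combined protocol and SAP*

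**What the plan says.** Section 4 (Interventions) gives the active arm as "Participants in the intervention group will receive laser acupuncture at predefined acupoints according to a standardized protocol" and the control as "The control group will receive usual care or sham treatment as specified". Section 1 sets the primary objective, to "evaluate the efficacy of laser acupuncture in reducing uremic pruritus in patients undergoing hemodialysis", and names no comparator. Section 2 calls the study randomized and controlled and adds: "Eligible participants will be allocated to intervention or control groups according to the study protocol". Section 5 says that the primary outcome "is change in pruritus severity measured by validated scales", without naming a scale or a rater. Section 6.2 says: "Between-group comparisons will be performed to evaluate treatment effects". Section 6.1 includes everyone randomized in the intention-to-treat analysis. Blinding is not mentioned in any section. Usual care appears only as one of the two control options, and the text does not say whether the laser arm receives it too.

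**The concern.** The comparator is half of any treatment contrast, and here two are offered for one control group. Pruritus severity may well be self-rated, and expectation and the attention that comes with repeated sessions can move a self-rated score. With usual care and no blinding, those influences are part of the estimated effect. With a credible sham and blinding, they largely cancel. The word efficacy in Section 1 fits either reading, and the intention-to-treat statement settles who is analysed but not what they are compared with. A positive primary result could therefore mean that the whole package helps or that the laser helps. A usual-care result could be reported as laser-specific without an obvious departure from the text.

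**Working it through.** **Is the choice made anywhere in the available text?** The sections that could settle it are:

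| Section | What it contributes |
|---|---|
| 1. Study Objectives | efficacy; no comparator |
| 2. Study Design | randomized, controlled; refers to the study protocol; nothing on blinding |
| 4. Interventions | two options for the control, with a reference to a specification |
| 5. Outcome Measures | change in severity; no scale, no rater |
| 6.1 Analysis Populations | all randomized participants |
| 6.2 Primary Outcome Analysis | comparison between groups; no comparator |

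The choice is not stated. The text does not contradict itself; it is silent. Sections 2 and 4 both point to a specification. Section 4 also refers to a standardized protocol and predefined acupoints that are not reproduced, so the file reads like a summary of fuller working documents. One part of the file was removed before review. None of this proves that the choice was made elsewhere, but all of it is consistent with that.

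**Does following the plan produce a wrong analysis?** Take each possibility in turn.

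- Usual care: the comparison validly estimates the total effect of laser acupuncture against usual care.
- Credible, blinded sham: it validly estimates the laser-specific effect.
- Some controls on each, or separate control groups: the wording does not exclude this. The comparison would then be a pooled or a multiple one, but randomization would still support it.

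None of these makes the primary test invalid. Misinterpretation needs a further step, namely claiming a laser-specific effect from an unblinded usual-care comparison, and no section commits the trial to that claim.

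**How large could the difference between the readings be?** The plan has no figure to reproduce. Only one input comes from the documents: "All statistical tests will be two-sided with a significance level of 0.05" (Section 6.5). Everything else is assumed:

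- two equal arms of *n* = 30, 40 or 60;
- no laser-specific effect;
- an expectation and attention shift of *d* = 0, 0.1, 0.2 or 0.4 SD in the change score.

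For a two-sample *t* test, the noncentrality is *d* / √(2/*n*) with 2*n* − 2 degrees of freedom. The probability wanted is that of exceeding the upper 2.5% critical value. At *d* = 0.4 the noncentrality is

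- *n* = 30: 0.4 / √(2/30) = 0.4 / 0.2582 = 1.55, df 58;
- *n* = 40: 0.4 / √(2/40) = 0.4 / 0.2236 = 1.79, df 78;
- *n* = 60: 0.4 / √(2/60) = 0.4 / 0.1826 = 2.19, df 118.

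Probability of a significant result favouring laser:

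| *n* per arm | *d* = 0 | 0.1 | 0.2 | 0.4 |
|---|---|---|---|---|
| 30 | 0.0250 | 0.0572 | 0.1154 | 0.3313 |
| 40 | 0.0250 | 0.0645 | 0.1408 | 0.4234 |
| 60 | 0.0250 | 0.0783 | 0.1912 | 0.5844 |

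A simulation of 100,000 trials per setting agrees (for example 0.3299, 0.4211 and 0.5850 at *d* = 0.4). It confirms the formula but adds no evidence about this trial.

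Under usual care, the columns with *d* above 0 are ordinary power to detect a total effect that is really there. The 2.5% column follows from assuming that a blinded sham removes the shift completely. Setting 58% beside 2.5% compares two different questions, so it does not measure an inflated error rate.

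**The case for a change.** The strongest reply is that a document labelled as the combined protocol and SAP should name its own comparator, and that a reference to a specification which the text does not contain settles nothing. That is fair as a comment on reporting. A reader of this text alone cannot say which effect the primary contrast estimates, and if the control is unblinded usual care, a report that speaks loosely of efficacy could mislead. The possibility of a mixed or multi-group control adds to this, because a choice of which groups to compare would then remain open.

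What does not stand is the step from unstated in this text to undecided in the trial. Unlike the choice of test or imputation method, the control condition cannot be picked after the outcomes are seen: it is whatever the control patients were given. Section 7 says the study "has received approval from the appropriate institutional review board", which makes it plausible, though not certain, that the control was described to the board.

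Nor would naming the control fix the contrast by itself, since the scale, assessment time and test are also left general. Writing it in would alter the approved protocol and might need ethics review. It would change neither the data collected nor the analysis performed.

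**Conclusion.** The observation is accurate: the available text does not say which control is used, whether it is single or mixed, what background care each arm receives, or who is blinded. It is missing detail, not an error in the design or the analysis. Whichever control was used, the randomized comparison is valid, and the control actually delivered determines how the result may be worded. A competent analyst will name it and limit the conclusion to match, claiming a laser-specific effect only against a credible, blinded sham.

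The consequence cannot be sized from the documents. The range of 6% to 58% rests wholly on assumed arm sizes and shifts; at a shift of 0.1 SD it is only 6% to 8%, against 2.5% with no shift.

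The conclusion assumes that the control was settled before patients were treated, as Section 4 implies. It would change if the trial were shown to have committed to a laser-specific claim without a blinded sham, or to have left open which of several control groups enters the primary comparison. The text shows neither.

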## 5. Outcome Measures

The **primary outcome** is change in pruritus severity measured by validated scales.

**Secondary outcomes** include quality-of-life measures and adverse events.

## 6. Statistical Analysis Plan (SAP)

### 6.1 Analysis Populations

All randomized participants will be included in the intention-to-treat (ITT) analysis. A per-protocol analysis may be conducted as a secondary analysis.

### 6.2 Primary Outcome Analysis

The primary outcome will be analyzed using appropriate statistical tests based on data distribution. Between-group comparisons will be performed to evaluate treatment effects.

### 6.3 Secondary Outcome Analyses

Secondary outcomes will be analyzed using suitable parametric or non-parametric methods. Repeated measures may be analyzed using appropriate models.

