### 6.4 Handling of Missing Data

Missing data will be handled using appropriate statistical methods, such as multiple imputation or last observation carried forward, depending on the nature and extent of missingness.

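### Does the SAP need its own safety analysis when adverse events fall only under the general rule for secondary outcomes?

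*Combined protocol and SAP*

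**What the plan says.** All the relevant text is in the combined protocol and SAP.

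- Section 1: "Secondary objectives include assessment of symptom severity, quality of life, and treatment safety".
- Section 5: secondary outcomes "include quality-of-life measures and adverse events".
- Section 6.1: "All randomized participants will be included in the intention-to-treat (ITT) analysis". It adds: "A per-protocol analysis may be conducted as a secondary analysis".
- Section 6.3: "Secondary outcomes will be analyzed using suitable parametric or non-parametric methods".
- Section 6.4 gives examples of missing-data methods, "such as multiple imputation or last observation carried forward, depending on the nature and extent of missingness".
- Section 6.5: "All statistical tests will be two-sided with a significance level of 0.05".

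Sections 6.1 to 6.5 name neither safety nor adverse events, and no section mentions a confidence interval. On the comparator, section 4 says: "The control group will receive usual care or sham treatment as specified".

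**The concern.** Adverse events do not behave like a pruritus or quality-of-life score. Someone has to decide whether to count participants or events, over which denominator, how to treat people who leave early, and whether to test at all. The SAP answers none of these for adverse events in particular.

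Three routes to a misleading safety statement then seem open.

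- The per-protocol set is undefined and is not restricted to efficacy. If it drops people who stop treatment, it drops those who stopped because of an event.
- LOCF is one of the named missing-data options. Applied to a yes/no event status, it counts everyone lost without an event as event-free.
- There is a significance level but no interval. With few events, a non-significant test could be read as evidence of safety although a large excess has not been excluded.

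At stake is whether the safety conclusion could be shaped by choices made once events by arm are known.

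**Working it through.** The plan states no figure to reproduce. The check has two parts: what the sections settle when read together, and how far the open choices could move a result.

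**What the sections settle**

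| Question | What the SAP gives | Left open |
|---|---|---|
| Who is analysed | Everyone randomised (6.1); per-protocol optional and secondary | Whether an optional per-protocol table would include events |
| Method | A suitable method for the outcome (6.3) | Counting unit; test or description |
| People lost | Two methods as examples, for missing data in general (6.4) | Whether event status is imputed at all |
| Error level | Two-sided 0.05 (6.5) | Whether an interval is shown |

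No entry in the middle column gives a wrong result for adverse events. An analyst who reports the number and proportion of participants with an event, by assigned arm, among all randomised, complies with every line.

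**How far the open choices could move a result**

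All inputs below are assumed, because the document gives no arm size, event rate or dropout.

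*Analysis set.* Take 30 per arm, with 5 laser and 2 control participants having an event. The risk difference is laser proportion minus control proportion. Suppose *k* of the five stop because of the event and nobody else is excluded:

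- All randomised (also per-protocol with *k* = 0): 5/30 − 2/30 = 16.7% − 6.7% = 10.0 points, Fisher p = 0.42
- *k* = 1: 4/29 − 2/30 = 13.8% − 6.7% = 7.1 points, p = 0.42
- *k* = 2: 3/28 − 2/30 = 10.7% − 6.7% = 4.0 points, p = 0.67
- *k* = 3: 2/27 − 2/30 = 7.4% − 6.7% = 0.7 points, p = 1.00

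The fall to 0.7 needs a definition of per-protocol that the document does not give, exclusions confined to laser participants with events, and the secondary analysis taken as the main one.

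*Participants lost.* Take 4 of 30 with an event in each arm, with all losses event-free. LOCF gives 4/30 − 4/30 = 0. Among those followed to the end or with an event:

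- 10 against 1 lost: 4/20 − 4/29 = 20.0% − 13.8% = 6.2 points, p = 0.70
- 6 against 2 lost: 4/24 − 4/28 = 16.7% − 14.3% = 2.4 points, p = 1.00
- 3 against 1 lost: 4/27 − 4/29 = 14.8% − 13.8% = 1.0 point, p = 1.00
- Equal loss: 0

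The largest shift needs 10/30 = 33% lost in one arm and 1/30 = 3% in the other. The followed-only figure is no neutral standard either. It drops event-free people with partial follow-up and keeps people lost after an event, so it tends to overstate incidence. Meanwhile the LOCF figure is numerically the ordinary proportion over all randomised, which any safety table would show.

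*Non-significance.* With 3 against 0 events at 30 per arm, Fisher's two-sided p is 2 × C(30,3)/C(60,3) = 2 × 4060/34220 = 0.237. The Newcombe 95% interval for the 10-point difference is −3.1 to 25.6 points. At 60 per arm it is −1.9 to 13.7, and at 100 per arm −1.2 to 8.5. A bare p-value would hide that width. But 6.5 sets a level for tests where tests are done; it neither requires a test of adverse events nor prevents an interval.

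**The case for a change.** The case for a change is reasonable. Safety is a stated objective, the counting unit and denominator are particular to adverse events, and even a fully specified analysis of the scales would not supply them. Fixing them before events by arm are seen would take a paragraph and a table, with no extra participants.

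What stands is the factual core: adverse events are reached only by a general sentence, and 6.1 names no separate safety set. A line giving the set, the measure, an interval and one main denominator would make the document clearer.

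What does not stand is that its absence harms the trial's conclusions. The natural main set, all randomised by assigned arm, restates 6.1. A treated-only set would add little: with assumed risks of 15% treated and 5% otherwise, and 10% of the laser arm never treated, the difference becomes 0.15 × 0.9 + 0.05 × 0.1 − 0.05 = 0.09, or 9 points instead of 10.

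A safety paragraph could also leave the same choices open. Forbidding LOCF while reporting events over all randomised yields the LOCF number. Showing two denominators without naming a main one keeps that choice open. Allowing Fisher's test beside a Newcombe interval can produce disagreement: 5/30 against 0/30 gives p = 0.052 with an interval of 2.0 to 33.6 points. Which interval to use is a matter of preference. Event definition, grading and collection window concern data collection rather than the choice of analysis.

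**Conclusion.** No change to the plan is called for. This is a gap in detail that a competent analyst fills by reporting participants with an event, by arm, among all randomised, with the numbers lost alongside. The wording permits that and sends nobody elsewhere.

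The gap is not peculiar to safety. Section 6.2 is just as general about the primary outcome, so adverse events are one instance of how the whole SAP is written, and a secondary one.

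The possible shifts run from 0 to about 9 points for the analysis set (10.0 to 0.7) and from 0 to 6.2 points for loss, at an assumed 30 per arm. Both vanish if nobody stops because of an event or if loss is equal between arms, and no difference in these two illustrations reaches significance. The figures depend on assumed counts and on a misreading of 6.1 or 6.4. They do not show that a rule as written gives a wrong safety result. The conclusion covers this document only; sections 2 and 4 refer to a schedule and treatment details set out in advance, and any fuller text behind them was not available.

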### 6.4 Handling of Missing Data

Missing data will be handled using appropriate statistical methods, such as multiple imputation or last observation carried forward, depending on the nature and extent of missingness.

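### Section 6.4 allows last observation carried forward in the primary analysis and gives no rule for choosing it; when dropout differs by arm, that method can exceed the 0.05 level

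*Combined protocol and SAP*

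**What the plan says.** Section 6.4 offers methods "such as multiple imputation or last observation carried forward, depending on the nature and extent of missingness". Both are examples, and other methods remain open. It gives no threshold or decision rule, no timing for the choice, no statement that the choice is blind, and no sensitivity analysis.

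The other sections do not close the gap:

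- Section 6.1: "All randomized participants will be included in the intention-to-treat (ITT) analysis". Patients with missing scores therefore have to be handled somehow.
- Section 6.2: "The primary outcome will be analyzed using appropriate statistical tests based on data distribution". No primary model is fixed that would settle the matter.
- Section 5: the primary outcome "is change in pruritus severity measured by validated scales", with no scale or time point named.
- Section 6.3: "Repeated measures may be analyzed using appropriate models". This is optional and stands under secondary outcomes.
- Section 6.5: "All statistical tests will be two-sided with a significance level of 0.05".

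Section 6.4 does not name the primary outcome, but it exempts no outcome. That LOCF may be used in the primary analysis comes from reading 6.1, 6.2 and 6.4 together.

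**The concern.** LOCF assumes that a patient's score stays at its last observed value. For an outcome defined as a change, a patient with no post-baseline score would get a change of zero if baseline is carried forward, and an early leaver is frozen part of the way through any improvement. Two situations bias the comparison when there is no true effect:

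1. Dropout differs by arm in amount or timing, and itch changes over time.
2. Dropout depends on the itch score, and does so differently by arm. No time trend is needed.

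The bias can favour or disfavour laser. Section 4 leaves the comparator open ("The control group will receive usual care or sham treatment as specified"). Under usual care patients would know their arm, so unequal dropout is possible, though not certain. At stake is whether the primary test holds its stated two-sided level.

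The unspecified choice adds a second weakness. Nobody can tell in advance which method the primary result will rest on.

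**Working it through.** **Inputs.** The plan supplies only the two-sided 0.05 level, so it has no derived figure to reproduce. Section 2 says only that "The study duration and assessment schedule are predefined". Everything else is my assumption: SD 2 points at each visit, within-patient correlation 0.6, four post-baseline visits, the same 2-point linear improvement in both arms (no true difference), a t-test on change, 30/40/60 patients per arm, and baseline carried forward when there is no post-baseline score. Dropout is random unless stated, and leavers are last seen at visits 0, 1, 2 or 3 equally often.

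**Bias.** A leaver keeps on average (0 + 0.25 + 0.50 + 0.75)/4 = 0.375 of the improvement and loses 0.625.

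LOCF bias = trend × share lost × difference in dropout proportion

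- Equal dropout: 2 × 0.625 × 0 = 0
- 10% vs 20%: 2 × 0.625 × 0.10 = 0.125 points
- 10% vs 30%: 2 × 0.625 × 0.20 = 0.25 points, favouring the arm with less dropout
- One post-baseline visit, 10% vs 30%: all improvement is lost, 2 × 1 × 0.20 = 0.40 points

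**From bias to type I error.** The SD of change is 2 × √(2 × (1 − 0.6)) = 1.789. At 40 per arm, SE = 1.789 × √(2/40) = 0.400. For 10% vs 30%, bias/SE = 0.25/0.400 = 0.625. Rejection ≈ P(Z > 1.96 − 0.625) + P(Z < −1.96 − 0.625) = 0.091 + 0.005 = 0.096. Simulation gives 0.094.

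**Simulated LOCF type I error** (20,000 trials per cell, Monte Carlo SE about 0.002):

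| Scenario, no true difference | 30 per arm | 40 per arm | 60 per arm |
|---|---|---|---|
| No trend, random 10% vs 30% | 0.051 | 0.051 | 0.052 |
| 2-point trend, 10% vs 15% | 0.050 | 0.055 | 0.053 |
| 2-point trend, 10% vs 20% | 0.057 | 0.062 | 0.066 |
| 2-point trend, 10% vs 30% | 0.081 | 0.094 | 0.116 |
| Same, everyone has one post-baseline score | 0.068 | 0.077 | 0.091 |
| 2-point trend, 20% in both arms, early in one and late in the other | 0.071 | 0.080 | 0.092 |
| One visit, 2-point improvement, 10% vs 30% | 0.142 | 0.173 | 0.240 |

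Random dropout equal in amount and timing (10%, 20% or 30%) gives 0.048–0.053. With no trend, but dropout driven by a high observed score at 10% vs 30%, the error runs from 0.076/0.081/0.102 (leaving probability raised above 0.5 or 1 SD over the visit mean) up to 0.101/0.122/0.156, depending on the rule. Adjusting for baseline does not rescue LOCF: the 10% vs 30% linear cell becomes 0.088/0.105/0.132.

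**Comparison.** Multiple imputation by arm with baseline adjustment gave 0.030–0.056 wherever dropout was random or driven by observed scores (4,000 trials per cell, SE about 0.003).

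**Real effects.** LOCF also shrinks a true effect that grows to the last visit, even with equal dropout p: a 2-point effect becomes 2 × (1 − 0.625p) = 1.75 at p = 0.20.

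**The case against.** The strongest reply has four parts.

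**The text does not commit to LOCF.** A reader might infer that the primary analysis will use LOCF. The documents do not support that: the methods are examples, and multiple imputation comes first. A reader might also infer that the method will be picked to suit the result. The documents tie the choice to missingness, not to results, and a choice made blind to arm and results does not by itself raise the error rate. What stands is that the blind choice is nowhere stated and LOCF is nowhere excluded.

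**The size is all assumption.** This is correct. A reader might infer that this trial's error rate will be inflated; nothing in the documents shows that. An unequal dropout percentage is not enough by itself, as the no-trend row shows. Nor does an equal percentage guarantee safety, as the early-versus-late row shows.

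**Carrying baseline forward is not stated.** Section 6.1 makes it plausible, because every randomized patient is included. Without it the 10% vs 30% figures fall, but stay above 0.05.

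**The remedy is not uniformly better.** This also stands. If dropout is driven by the unseen score, with no trend and 10% vs 30%, multiple imputation reaches 0.115 at worst while LOCF stays at 0.053–0.068. With a 2-point trend as well, under the 1 SD rule, imputation gives 0.065/0.076/0.116 and LOCF 0.073/0.081/0.092. That is a reason to add a missing-not-at-random analysis. It does not make LOCF a sound primary method, because LOCF can also fail under random or observed-score dropout, where imputation held the level.

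**Conclusion.** The point holds as a conditional one. The plan permits LOCF in the primary intention-to-treat analysis, and LOCF can break the 0.05 level when the dropout process differs by arm in the ways described. The absence of a rule is certain from the text; the size of the consequence is not. Under the stated assumptions it runs from nothing (same dropout process in both arms) through about 0.06 (10% vs 20%) to about 0.08/0.09/0.115 (10% vs 30%), and about 0.14/0.17/0.24 with a single post-baseline visit and the same 2-point improvement. The direction is not fixed: when both arms improve, the arm with less dropout gains. The text should be corrected before outcomes are compared by arm, because the primary result may depend on it and the change is cheap.

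**What to change.** In section 6.4, remove LOCF as an option for the primary analysis, and remove the clause that makes the method depend on the missingness seen. Before outcomes are compared by arm, state one primary method valid under missing at random. Suggested wording:

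> Missing scores on the primary scale will be multiply imputed separately by arm from the baseline score and any observed post-baseline scores, for all randomized participants. In each imputed data set the baseline-adjusted mean difference in change at the primary time point will be estimated by linear regression, and the estimates pooled by Rubin's rules.

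The pooled estimate has to be named because section 6.2 leaves the test open, and Rubin's rules do not directly pool a rank test. A mixed model on all observed scores, with baseline included as an outcome, is an acceptable alternative; I did not simulate it. Add one prespecified missing-not-at-random sensitivity analysis, such as delta-adjusted imputation over a stated range. LOCF may stay as a labelled sensitivity analysis. Section 5 must name the primary scale and time point, or the text cannot be applied.

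**Cost.** A few sentences and slightly more analysis work; no new patients or data. In simulation, confidence intervals were wider than under LOCF by about 7% to 18% with random dropout and 13% to 42% with dropout driven by observed scores. Unadjusted imputation was somewhat conservative in small samples (as low as 0.029 at 30 per arm).

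LOCF's power depends on which arm loses more patients. Take a real 1.5-point effect with a 1-point control-arm trend, so a 2.5-point improvement on laser:

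- 10% dropout on laser, 30% on control: the expected LOCF difference is 2.5 × (1 − 0.0625) − 1 × (1 − 0.1875) = 1.53. LOCF power is about 0.90/0.96/0.995, partly through bias; imputation gave 0.77/0.91/0.99.
- 30% on laser, 10% on control: the difference is 2.5 × (1 − 0.1875) − 1 × (1 − 0.0625) = 1.09. LOCF power is only about 0.61/0.75/0.90.

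The apparent power advantage of LOCF is therefore not something to plan on.
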